11. APPENDICES

APPENDIX1 Partial Date Conventions

ALGORITHM FOR TREATMENT EMERGENCE OF ADVERSE EVENTS:

START DATE	STOP DATE	ACTION
Known	Known/Partial /Missing	If start date < study drug start date, then not TEAE If start date >= study drug start date and < end of treatment + 15 in days , then TEAE
Partial, but known components show that it cannot be on or after study drug start date	Known/Partial /Missing	Not TEAE
Partial, could be on or after study drug start date	Known	If stop date < study drug start date, then not TEAE If stop date >= study drug start date, then TEAE
	Partial	Impute stop date as latest possible date (i.e., last day of month if day unknown or 31st December if day and month are unknown), then: If stop date < study drug start date, then not TEAE If stop date >= study drug start date, then TEAE
	Missing	Assumed TEAE
Missing	Known	If stop date < study drug start date, then not TEAE If stop date >= study drug start date, then TEAE
	Partial	Impute stop date as latest possible date (i.e., last day of month if day unknown or 31st December if day and month are unknown), then: If stop date < study drug start date, then not TEAE If stop date >= study drug start date, then TEAE
	Missing	Assumed TEAE

Sponsor: Boston Pharmaceuticals, Inc.
 Protocol Number: BOS-589-201
 Version and Date: Version 1.2 12NOV2020

ALGORITHM FOR PRIOR / CONCOMITANT MEDICATIONS:

START DATE	STOP DATE	ACTION
Known	Known	If stop date < study drug start date, assign as prior If stop date >= study drug start date and start date <= end of treatment + 15 in days, assign as concomitant
	Partial	Impute stop date as latest possible date (i.e., last day of month if day unknown or 31 st December if day and month are unknown), then: If stop date < study drug start date, assign as prior If stop date >= study drug start date and start date <= end of treatment + 15 in days, assign as concomitant
	Missing	If stop date is missing could never be assumed a prior medication If start date <= end of treatment + 15 in days, assign as concomitant
Partial	Known	Impute start date as earliest possible date (i.e., first day of month if day unknown or 1 st January if day and month are unknown), then: If stop date < study drug start date, assign as prior If stop date >= study drug start date and start date <= end of treatment + 15 in days, assign as concomitant
	Partial	Impute start date as earliest possible date (i.e., first day of month if day unknown or 1 st January if day and month are unknown) and impute stop date as latest possible date (i.e., last day of month if day unknown or 31 st December if day and month are unknown), then: If stop date < study drug start date, assign as prior If stop date >= study drug start date and start date <= end of treatment + 15 in days, assign as concomitant
	Missing	Impute start date as earliest possible date (i.e., first day of month if day unknown or 1 st January if day and month are unknown), then: If stop date is missing could never be assumed a prior medication If start date <= end of treatment + 15 in days, assign as concomitant
Missing	Known	If stop date < study drug start date, assign as prior If stop date >= study drug start date, assign as concomitant

Sponsor: Boston Pharmaceuticals, Inc.
Protocol Number: BOS-589-201
Version and Date: Version 1.2 12NOV2020

START DATE	STOP DATE	ACTION
	Partial	Impute stop date as latest possible date (i.e., last day of month if day unknown or 31 st December if day and month are unknown), then: If stop date < study drug start date, assign as prior If stop date >= study drug start date, assign as concomitant
	Missing	Assign as concomitant

APPENDIX2 The Bristol Stool Form Scale

Bristol Stool Chart

Type 1		Separate hard lumps, like nuts (hard to pass)
Type 2		Sausage-shaped but lumpy
Type 3		Like a sausage but with cracks on its surface
Type 4		Like a sausage or snake, smooth and soft
Type 5		Soft blobs with clear-cut edges (passed easily)
Type 6		Fluffy pieces with ragged edges, a mushy stool
Type 7		Watery, no solid pieces. Entirely Liquid

Sponsor: Boston Pharmaceuticals, Inc.
Protocol Number: BOS-589-201
Version and Date: Version 1.1 27MAR2019

**A PHASE 2A, RANDOMIZED, DOUBLE-BLIND,
PLACEBO-CONTROLLED, MULTICENTER STUDY TO
EVALUATE THE EFFICACY, SAFETY, AND
TOLERABILITY OF BOS-589 IN THE TREATMENT OF
PATIENTS WITH DIARRHEA-PREDOMINANT
IRRITABLE BOWEL SYNDROME (IBS-D)**

Statistical Analysis Plan

**VERSION 1.1
DATE OF PLAN:**

Mar 27, 2020

STUDY DRUG:
BOS-589

PREPARED FOR:
Boston Pharmaceuticals, Inc.

Sponsor: Boston Pharmaceuticals, Inc.
Protocol Number: BOS-589-201
Version and Date: Version 1.1 27MAR2019

Approval Signature Page: PPD Inc.

PPD

PPD

PPD

Sponsor: Boston Pharmaceuticals, Inc.
Protocol Number: BOS-589-201
Version and Date: Version 1.1 27MAR2019

Approval Signature Page: Boston Pharmaceuticals, Inc.

PPD

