8.5.1 Definition of Adverse Events

An AE is any untoward medical occurrence in a patient or clinical study participant, temporally associated with the use of investigational product, whether or not considered related to the investigational product. An AE can therefore be any unfavorable and unintended sign (including an abnormal laboratory finding), symptom, or disease (new or exacerbated) temporally associated with the use of investigational product.

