8.5.5 Time Period and Frequency for Event Assessment and Follow-up

All AEs will be collected from the signing of the ICF until the End-of-Study Follow-up visit.

Whenever possible, all AEs should be followed until satisfactory resolution or until the site Investigator deems the event to be chronic or the patient is stable.

All SAEs will be recorded and reported to the sponsor or designee within 24 hours, whether considered investigational product related or not, and must include an assessment of if there is a reasonable possibility that the investigational product caused the event. The Investigator will also submit any updated SAE data to the sponsor within 24 hours of it being available.

Investigators are not obligated to actively seek AEs or SAEs after conclusion of the study participation. However, if the Investigator learns of any SAE, including a death, at any time after a patient has been discharged from the study, and he or she considers the event to be reasonably related to the investigational product or study participation, the Investigator must promptly notify the sponsor.

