8.5.6 Adverse Event Reporting

At each study visit, patients will be evaluated for new AEs and the status of existing AEs. Care will be taken not to introduce bias when evaluating for AEs. The Investigator should use open-ended questions when soliciting information from a patient regarding AEs, followed by appropriate questions that clarify the patient's verbatim description of AEs or change in concomitant medications.

When an AE occurs, it is the responsibility of the Investigator to review all documentation (e.g., hospital progress notes, laboratory reports, and diagnostics reports) related to the event. The Investigator will attempt to establish a diagnosis of the event based on signs, symptoms, and/or other clinical information. Whenever possible, the diagnosis (not the individual signs/symptoms) will be documented as the AE.

The Investigator will then record all relevant AE information in the CRF. It is not acceptable for the Investigator to send photocopies of the patient's medical records in lieu of completion of the CRF page. New or updated information will be recorded in the originally completed CRF. However, there may be instances when copies of medical records for certain cases are requested. In this case, all patient identifiers, with the exception of the patient number, will be redacted on the copies of the medical records before submission.

If a patient dies during participation in the study or during a recognized follow-up period, the Investigator will provide a copy of any postmortem findings, including histopathology when available.

If a site receives report of a new SAE from a study patient or receives updated data on a previously reported SAE after database lock of the electronic data capture (EDC) system, then the site can report this information on a paper SAE form or to the sponsor by telephone. See the Study Manual for additional information on SAE reporting.

The study sponsor, or designee, will be responsible for notifying all applicable regulatory authorities of any required safety events in compliance with country-specific regulatory requirements. In addition, the sponsor must notify applicable regulatory authorities and all participating Investigators of suspected unexpected serious adverse reactions (SUSARs), from clinical trials or any other source.

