9.4.2 Safety Analyses

9.4.2.1 Adverse Events

Adverse events will be recorded from the time of consent until the Day 43/End-of-Study Follow-up visit. The number and percentage of patients with AEs will be displayed by system organ class and preferred term using Medical Dictionary for Regulatory Activities (MedDRA) Version 20.0 or higher, by study treatment. Summaries in terms of severity and relationship to investigational product will also be provided. All SAEs will be summarized in a similar manner. Patient listings of all AEs causing discontinuation of investigational product and all SAEs will be produced.

All AEs will be listed for individual patients showing both verbatim and preferred terms. Separate summaries of treatment-emergent SAEs and treatment-emergent AEs (TEAEs) related to investigational product will be generated.

Any event reported on the CRF that occurs on at the time of or after the initiation of investigational product is defined as treatment-emergent. Additionally, an AE that is reported to have started on Day 1 without an associated onset time will be assumed to have occurred after the initiation of investigational product. Hence, AEs occurring on Day 1 with no associated onset time will be assumed to be treatment emergent.

Serious AEs associated with a protocol-specified procedure and occurring after the time of consent but before administration of first dose of investigational product will be defined as non-treatment-emergent AEs (NTEAEs).

All safety analyses will be performed in the Safety Analysis Dataset.

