9.1. Adverse Events

AEs starting after the informed consent date until the Day 43/End of Study Follow-up visit will be recorded. AE assessments will include severity (mild, moderate, severe), relationship to study drug (related or not related), and seriousness. AEs with a missing severity will be classified as severe. AEs with a missing causality will be classified as related. AEs with missing seriousness will be classified as serious.

Any event reported on the CRF that occurs on or after the initiation of study drug is defined as a treatment-emergent adverse event (TEAE). Guidelines for categorizing an event as treatment-emergent based on start and stop dates and times are in Appendix 1. Additionally, an AE that is reported to have started on Day 1 without an associated onset time will be assumed to have occurred after the initiation of study drug. Hence, AEs occurring on Day 1 with no associated onset time will be assumed to be treatment emergent. SAEs associated with a protocol specified procedure and occurring after the time of consent but before administration of first dose of study drug will be defined as non-treatment emergent AEs (NTEAEs) and will be excluded from summary tables but will appear in listings flagged as NTEAE.

On a summary table, the number and percentage of patients in each of the following categories will be summarized by cohort following the cohort display in section 5.9:

- Any TEAE
- Any TEAEs related to study drug
- Any moderate or severe TEAEs
- Any moderate or severe TEAEs related to study drug
- Any treatment-emergent SAEs
- Any treatment-emergent SAEs related to study drug
- Any TEAEs causing discontinuation of study drug
- Any TEAEs with outcome of death
- Any TEAEs leading to withdrawal from the study

AEs will be coded to a SOC and PT using MedDRA (the version used will be defined in the study data management plan).

For summaries of TEAEs by SOC and PT, a patient will be counted once within an SOC, even if the patient experienced more than one TEAE within a specific SOC (likewise for PT). TEAEs will be ordered by descending frequency for overall SOC incidence followed by descending frequency of overall PT incidence. Summaries of TEAEs by SOC and PT will include the following:

- All TEAEs
- All TEAEs by severity
- All moderate or severe TEAEs
- All TEAEs related to study drug
- All treatment-emergent SAEs

Sponsor: Boston Pharmaceuticals, Inc.
Protocol Number: BOS-589-201
Version and Date: Version 1.2 12NOV2020

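### An adverse event that starts before first dose and worsens on study drug is not treatment-emergent under the SAP, so unless the site opens a new record it is missing from every AE summary table

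*SAP*

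**What the plan says.** Protocol 8.5.5 sets the collection window: "All AEs will be collected from the signing of the ICF until the End-of-Study Follow-up visit". The Schedule of Activities allows screening from Day -36, so the pre-dose part of that window can last several weeks.

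The SAP definition in 9.1 turns on timing: "Any event reported on the CRF that occurs on or after the initiation of study drug is defined as a treatment-emergent adverse event (TEAE"). Protocol 9.4.2.1 has the same rule: "Any event reported on the CRF that occurs on at the time of or after the initiation of investigational product is defined as treatment-emergent". Neither mentions an event that started earlier and got worse.

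SAP 9.1 sends the reader to Appendix 1 for the classification. Its first row covers fully known start dates with any stop date: "If start date < study drug start date, then not TEAE". The second row covers a start date described as "Partial, but known components show that it cannot be on or after study drug start date", and it too gives not TEAE for any stop date. Only where a partial start date is ambiguous, or the start date is missing, does the stop date decide: "If stop date >= study drug start date, then TEAE". If the stop date is missing as well, the event is taken to be a TEAE.

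On recording, Protocol 8.5.6 says "New or updated information will be recorded in the originally completed CRF". Protocol 8.5.1, however, includes within the AE definition any "symptom, or disease (new or exacerbated) temporally associated with the use of investigational product".

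**The concern.** A patient may report a mild event in run-in that continues past Day 1 and becomes severe or serious on study drug. That worsening is what a safety table should pick up, yet under Appendix 1 the event stays outside the TEAE set because its start date is pre-dose.

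The incidence of AEs, SAEs, discontinuations for AEs and treatment-related severe AEs is a primary endpoint (Protocol Section 3, SAP Section 2). Every AE summary in SAP 9.1, both the overview and the tables by system organ class and preferred term, is confined to TEAEs or treatment-emergent SAEs. Any on-drug worsening excluded from the TEAE set therefore lowers the tabulated incidence of that endpoint. With 44 patients per cohort, a single event is visible in the percentages.

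**Working it through.** No power or alpha figure bears on this, and the plan states no number to reproduce. The check is to apply the Appendix 1 rows to concrete cases. Take first dose as Day 1 and last dose as Day 28. The upper limit for a known start date is then before Day 28 + 15 = Day 43.

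| Case | Appendix 1 result |
|---|---|
| Known start Day -10, becomes severe or serious Day 12, stops Day 20 | not TEAE |
| Same event, still ongoing | not TEAE |
| Partial start that must be pre-dose, ongoing | not TEAE |
| Partial start that could be on or after first dose, stops Day 20 | TEAE |
| Start missing, stops Day 20 | TEAE |
| Start missing, stops before first dose | not TEAE |
| Worsening entered as a separate AE starting Day 12 (12 < 43) | TEAE |

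Three things follow.

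1. Worsening changes the result in no row. For a known or necessarily pre-dose start, nothing that happens after first dose can make the event a TEAE.
2. The outcome for the first case depends on how the site records it. Kept on the existing record, it is not a TEAE; entered as a new record, it is. Protocol 8.5.6 leans towards the existing record, and no section asks for a new one.
3. An event with a missing start date that stops after first dose is counted, while a fully dated event with a documented on-drug worsening is not.

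The SAP handles comparable cases differently elsewhere. For ECG and vital signs (SAP 9.3), a patient already abnormal at baseline counts again if a later result is at least one grade worse. AEs have no such rule. Protocol 9.4.2.1 also promises a summary of all SAEs. SAP 9.1 tabulates only treatment-emergent ones, and SAP 3.2 does not list this as a change from the protocol.

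Size per patient, from the planned 44 per cohort:
- one cohort: 1/44 = 2.3 percentage points;
- pooled active group: 1/(44 + 44) = 1/88 = 1.1 percentage points.

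The number of such patients would be the cohort size times the share with an AE ongoing at first dose times the share of those who worsen on drug. The documents give neither share.

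**The case against.** The strongest reply is that the link through recording practice is an inference. The sentence in Protocol 8.5.6 says where follow-up information goes; it does not say that an exacerbation is an update and not a new event. Protocol 8.5.1 includes exacerbation in the AE definition, and Protocol 7.1 says a new clinically relevant finding after enrollment is reported as an AE. A site could reasonably open a new record, and the event would then be a TEAE. This stands as a limit: the CRF completion instructions are not in these documents, so the practice is unknown. It does not remove the gap, because the classification then rests on site habit.

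Several stronger readings are tempting and are not supported:

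- A reader might infer that such an event survives only in listings in every respect. SAP 6.2 summarizes discontinuation of study drug and of the study by cohort with reasons, regardless of TEAE status, so a discontinuation caused by the worsening is still counted there. Laboratory, ECG and vital-sign tables also do not depend on AE start dates. The SAP 9.1 listings of all SAEs, deaths and AEs causing discontinuation would show the case, though without an incidence by cohort.
- A reader might infer that start date alone decides for all events. For ambiguous partial or missing start dates the stop date decides.
- Constipation is a poor example: entry requires an average BSFS of at least 5.0 over the final 7 run-in days. Worsening abdominal pain is also tabulated by cohort through the weekly WAP scores.
- A reader might infer a bias that makes active cohorts resemble placebo. That follows only if the drug causes the worsening, which is unknown.
- A patient count can be produced only from assumed rates. If 15% to 30% of patients had an AE ongoing at first dose and 10% to 20% of those worsened, the shares would be 0.15 × 0.10 = 1.5% and 0.30 × 0.20 = 6%, or 0.66 to 2.64 patients of 44. Nothing in the documents supports those rates, and the range covers any worsening, not just severe or serious events.

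**Conclusion.** The gap is real but narrow. It concerns an AE whose start is known, or must be, before first dose, that is ongoing at first dose, worsens in severity or becomes serious on drug, and is not entered as a new record. Such an event is absent from every AE summary table in SAP 9.1 and appears only in the AE listings. A resulting discontinuation is still counted in the SAP 6.2 disposition summary.

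The consequence is a possible undercount of AE, SAE and related severe AE incidence in the primary safety endpoint. How many patients are affected cannot be determined from the documents. The conclusion rests on the stated classification rule, the absence of a worsening clause and the absence of any instruction to open a new record; it does not depend on an assumed event rate. It should be corrected because the endpoint is primary and the remedy is small.

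**What to change.** In SAP 9.1 and Appendix 1, define a TEAE as an event with onset on or after first dose, or an event with onset before first dose that increases in severity or becomes serious on or after first dose. Change the Appendix 1 rows for known and necessarily pre-dose start dates to match.

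In the CRF completion instructions, ask sites to enter such a worsening as a new AE record with its own start date. Both changes are needed: the definition states the intent, and the new record supplies the date that lets the rule be applied.

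The cost is about two sentences in the SAP and one site instruction. TEAE counts may rise slightly. A patient is counted once per system organ class and preferred term, so the extra record does not double-count anyone in those tables. No efficacy analysis or sample-size figure changes.

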4.1.3 Replacement of Patients

Patients who sign the ICF and are randomized but do not receive the investigational product may be replaced. Once randomized, patients who have received at least 1 dose of investigational product and are withdrawn from therapy before completing 28 days of dosing or are discontinued from the study for any reason will not be replaced.

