7 DISCONTINUATION / WITHDRAWAL

7.1 Discontinuation of Investigational Product

A patient may discontinue from study treatment at any time at his or her own request or may be withdrawn at any time at the discretion of the Investigator for safety, behavioral, or administrative reasons. Discontinuation from the investigational product does not mean discontinuation from the study, and remaining study procedures should be completed as indicated by the study protocol. If a clinically significant finding is identified (including, but not limited to, changes from baseline) after enrollment, the Investigator or qualified designee will determine if any change in patient management is needed. Any new clinically relevant finding will be reported as an AE.

Upon investigational product discontinuation, patients should complete all procedures collected in the Day 29/End-of-Treatment visit as applicable per the Schedule of Activities ([Section 1.3](#)).

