5.2. Reference Dates

Reference dates are defined as follows:

- Screening date is defined as the electronic case report form (eCRF) provided visit date on which a patient was screened for trial entry.
- Informed consent date is defined as the eCRF provided date of informed consent from the informed consent page.
- Run-in period start date is defined as earliest date of eCRF provided visit date from the Run-in period page.
- Run-in period end date is defined as eCRF provided date of randomization -1 from the randomization page.
- Treatment start date is defined as the date of first dose of any study drug.
- Treatment end date is defined as the date of last dose of any study drug.
- Age will come directly from the eCRF which is integrated from IWRS based on the informed consent date.

Sponsor: Boston Pharmaceuticals, Inc.
Protocol Number: BOS-589-201
Version and Date: Version 1.2 12NOV2020

- Safety data, such as AEs and laboratory assessments, will use the treatment start date as a reference date.
- Efficacy data will use the treatment start date as a reference date.
- Study day will be based on treatment start date as a reference date. Study Day 1 will be the day patients start the first dose of study drug.

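### SAP 9.1 and SAP Appendix 1 set different end limits for treatment-emergent adverse events, and the Appendix 1 limit can close before adverse-event collection does

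*SAP*

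**What the plan says.** Protocol 9.4.2.1 sets the collection period: "Adverse events will be recorded from the time of consent until the Day 43/End-of-Study Follow-up visit". The same section says that an event at the time of or "after the initiation of investigational product is defined as treatment-emergent". It gives no end date.

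SAP 9.1 (version 1.2) repeats this open-ended definition: "Any event reported on the CRF that occurs on or after the initiation of study drug is defined as a treatment-emergent adverse event (TEAE"). It then adds: "Guidelines for categorizing an event as treatment-emergent based on start and stop dates and times are in Appendix 1".

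The Appendix 1 table treats events by how complete their start date is:

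- **Known start date.** Before first dose, the event is not a TEAE. It is a TEAE on this condition: "If start date >= study drug start date and < end of treatment + 15 in days". No action is given for a later start.
- **Partial or missing start date.** Unless the known parts of the date rule out an onset on or after first dose, the event is a TEAE when its stop date is on or after first dose, or when the stop date is missing. There is no upper limit.

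SAP 5.2 fixes the reference point: "Treatment end date is defined as the date of last dose of any study drug". SAP 9, however, uses the phrase end of treatment for the Day 29/early-termination visit.

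**The concern.** Two parts of the current SAP give different answers for the same event, so two programmers could build different TEAE tables from the same data. The protocol's open definition does not settle the matter, because Protocol 9.4 gives the SAP precedence on analysis details. SAP 3.2, which lists changes from the protocol, does not mention a TEAE window.

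The incidence of adverse events and serious adverse events is a primary endpoint, and every adverse-event summary table in SAP 9.1 is restricted to TEAEs. An event or SAE beyond the Appendix 1 limit would therefore be missing from all of those tables, although Protocol 9.4.2.1 calls it treatment-emergent.

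Onsets dated to the End-of-Study visit are foreseeable. Laboratory tests and vital signs are scheduled for that visit, and Protocol 8.4.3 and 8.4.5 have clinically significant or relevant findings recorded as adverse events.

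**Working it through.** The plan gives no figure for this window, so there is none to reproduce. The check is date arithmetic.

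**Inputs**

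- First dose is Day 1 and there is no Day 0 (SAP 5.2 and 5.3).
- Planned last dose is Day 28 (Schedule of Activities; Protocol 4.1.3 refers to patients "withdrawn from therapy before completing 28 days of dosing").
- End of treatment is the last dose (SAP 5.2). The alternative reading is the Day 29 visit (SAP 9).
- The End-of-Study visit is Day 43 ± 3, that is Days 40 to 46 (Schedule of Activities).

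**Formulas.** Let L be the study day of end of treatment and V the day of the End-of-Study visit. The inequality is strict, so:

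- last counted onset day = L + 15 − 1 = L + 14
- collected days not counted = max(0, V − (L + 14))

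| L | Last counted onset | V = 40 | V = 42 | V = 43 | V = 46 |
|---|---|---|---|---|---|
| 28 (completer, last dose) | Day 42 | 0 | 0 | 1 | 4 |
| 29 (if the Day 29 visit is meant) | Day 43 | 0 | 0 | 0 | 3 |
| 21 (early stopper) | Day 35 | 5 | 7 | 8 | 11 |
| 14 (early stopper) | Day 28 | 12 | 14 | 15 | 18 |
| 7 (early stopper) | Day 21 | 19 | 21 | 22 | 25 |

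For a completer the loss is 0 to 4 days. For an early stopper followed to Day 43 it is 22 of 43 days (51%) with last dose on Day 7, and 15 of 43 days (35%) with last dose on Day 14. Under the open-ended definition in SAP 9.1 the loss is 0 days in every row.

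**Are early stoppers followed that long?** The protocol points both ways. Section 7.1 says "Discontinuation from the investigational product does not mean discontinuation from the study, and remaining study procedures should be completed", and section 6.5 has a patient who stops permanently after a dose reduction followed to the end of the study. Sections 4.1 and 8.1 describe the Day 43 visit only for patients who complete the Treatment Phase or Visit 7. The three early-stopper rows are therefore conditional, and those passages need to be reconciled.

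**Consistency within Appendix 1.** A late event with no start date counts, while the same event with a known date does not meet the condition. The medication algorithm in the same appendix includes starts up to and including end of treatment + 15 days. With last dose on Day 28, a drug started on Day 43 to treat an event would be concomitant, while the event itself would fall outside the TEAE condition.

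**The case against.** The strongest reply is that SAP 9.1 is the definition and Appendix 1 only an aid. The appendix is headed as a set of partial-date conventions, SAP 9.1 calls its content guidelines, and it never labels a late event as not treatment-emergent. On that reading nothing is excluded. This stands to the extent that exclusion is not certain. It does not remove the conflict, because SAP 9.1 sends the reader to Appendix 1 for this very decision and the row used for fully dated events carries a limit that the definition lacks.

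A bounded window is also a legitimate choice, and last dose plus 14 days matches the two-week follow-up. That is fair, but a window should then be declared and stated the same way throughout. It is neither.

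The practical loss is limited. SAP 9.2 and 9.3.3 summarize laboratory and vital-sign values at Day 43, and worst post-baseline values, without using the TEAE flag. All adverse events and all SAEs are listed. No hypothesis test is planned for safety. All of this stands, and it holds down the size of the problem in completers. It does not put a late event into an adverse-event incidence table.

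Three stronger readings are tempting and the documents do not support them:

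- That everything first reported at the End-of-Study visit drops out. The rule works on onset, so an event with onset on Days 29-42 that is first reported at that visit still counts.
- That early stoppers certainly lose weeks of events. This depends on follow-up to Day 43, on which the protocol conflicts.
- That the loss would differ between arms. No figure in the documents bears on this.

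**Conclusion.** The contradiction is certain and sits in the current SAP: an open-ended TEAE definition in SAP 9.1 and Protocol 9.4.2.1, against a date limit in Appendix 1 that applies to known start dates only, with later known dates left unassigned.

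Exclusion of events follows if Appendix 1 is applied as the operating rule. On that assumption the effect in completers is small and confined to onsets dated Day 43 or later, or Day 44 or later if end of treatment means the Day 29 visit. It is substantial only for early stoppers who remain under observation. The point deserves correction because the tables concerned are the only adverse-event summaries for a primary endpoint.

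**What to change.** In the TEAE algorithm of SAP Appendix 1, delete the upper bound (fifteen days after end of treatment) from the known-start-date row. Any recorded event with onset on or after first dose is then a TEAE. Known, partial and missing dates follow the same open-ended principle, and the appendix agrees with SAP 9.1 and Protocol 9.4.2.1.

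Deleting the bound is better than replacing it with a cap at the End-of-Study visit. Such a cap would be undefined for a patient without that visit, and it would not match either open-ended definition.

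If the sponsor wants a bounded on-drug window, it can be presented as an additional, separately labelled table.

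The cost is one SAP line and one programming condition, with no new data. TEAE counts may rise slightly.

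### SAP Appendix 1 classifies Day 1 adverse events by calendar date alone, while SAP 9.1 classifies them by time of first dose, and the SAP does not say which rule prevails

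*SAP*

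**What the plan says.** Protocol 9.4.2.1 sets the definition: "Any event reported on the CRF that occurs on at the time of or after the initiation of investigational product is defined as treatment-emergent". SAP 9.1 repeats it in nearly the same terms. Both sections add a default for Day 1: an event with no onset time is assumed to have begun after dosing and so counts as treatment-emergent.

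SAP 9.1 has a separate rule for serious events caused by a protocol-specified procedure before the first dose. These are non-treatment-emergent (NTEAE), stay out of the summary tables and are flagged in the listings.

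For the mechanics, SAP 9.1 points elsewhere: "Guidelines for categorizing an event as treatment-emergent based on start and stop dates and times are in Appendix 1". The Appendix 1 row for a known start date has two conditions: "If start date < study drug start date, then not TEAE", and otherwise "If start date >= study drug start date and < end of treatment + 15 in days , then TEAE". No row of that table mentions a time.

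The comparator in that row is a date. SAP 5.2 states: "Treatment start date is defined as the date of first dose of any study drug". It also states: "Study Day 1 will be the day patients start the first dose of study drug". Day 1 therefore includes the hours before dosing.

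**The concern.** Appendix 1 is where SAP 9.1 says times are handled, and it does not handle them. A programmer who follows the Appendix 1 table and one who follows the text of SAP 9.1 will class the same event differently if it began on Day 1 before dosing and its onset time was recorded. Neither would be departing from the SAP.

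The incidence of adverse events is listed under the primary endpoints in SAP section 2, so the rule that produces the counts should have one reading. An event that began before the first dose cannot be an effect of the drug. Counting it as treatment-emergent raises the reported incidence slightly, for a reason unrelated to treatment. For a procedure-related SAE the two rules give classes that exclude each other: in the summary tables under Appendix 1, out of them under SAP 9.1.

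**Working it through.** The plan states no figure to reproduce. The check is to run both rules on the same cases.

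**Step 1: classify five cases.** All have a known start date; first dose is on Day 1.

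| Onset | Appendix 1, known-start row | SAP 9.1 |
|---|---|---|
| Day -1 | not TEAE | not TEAE |
| Day 1, recorded time before first dose | **TEAE** | **not TEAE** |
| Day 1, no time recorded | TEAE | TEAE |
| Day 1, recorded time after first dose | TEAE | TEAE |
| Day 2 | TEAE | TEAE |

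The rules disagree on one case only. The upper limit in the Appendix 1 row (end of treatment plus 15 days) never removes a Day 1 event, so it plays no part here.

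**Step 2: can the case occur?** Adverse events are collected from consent (protocol 8.5.5). Protocol 8.7 schedules a predose PK blood draw on Day 1, and the first dose is given on site (protocol 6.6). An event between arrival and dosing is possible. The Schedule of Activities also places laboratory and biomarker samples on Day 1, but does not time them against the dose.

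**Step 3: size.** The documents give no rate, so these are assumptions: a share q = 0.5% to 5% of patients has a timed pre-dose event on Day 1, independent of a true any-TEAE incidence p = 20% to 40%, with the same q in every arm.

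- Observed incidence = p + (1 − p)q, so extra patients = N(1 − p)q.
- Per cohort of 44: from 44 × 0.6 × 0.005 = 0.13 to 44 × 0.8 × 0.05 = 1.76.
- Over 132 patients: from 132 × 0.6 × 0.005 = 0.40 to 132 × 0.8 × 0.05 = 5.28.
- A true difference of 20 points (40% against 20%) becomes 20 × (1 − q), that is 19.9 to 19.0 points.
- One patient wrongly added to a table row moves it by 1/44 = 2.3 points in a cohort, or 1/88 = 1.1 points in the pooled active group.

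The factor (1 − p) is there because a patient with another TEAE is already in the any-TEAE row. Rows for single preferred terms can still change for such a patient.

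**Step 4: add an onset-time condition for Day 1.** A recorded time before the first dose becomes not TEAE and a missing time stays TEAE. The rules then agree on all five cases.

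**The case against.** The best defence is that SAP 9.1 is the operative definition and Appendix 1 only supports it. The appendix is titled as a set of partial-date conventions, and SAP 9.1 calls its content guidelines. SAP 9.1 also states the specific table consequence for pre-dose procedure-related SAEs, and a specific rule reasonably overrides a general one. On that reading nothing is misclassified.

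This stands in part: the intended rule can be recovered from SAP 9.1. It does not remove the conflict. Despite its title, the appendix has a row for fully known start dates, and SAP 9.1 names it as the place for times. No order of precedence inside the SAP is given. The protocol cannot settle the matter, because protocol 9.4 gives the SAP precedence on analysis details.

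One could also read the wording of SAP 9.1 (on or after initiation) as meaning the day of initiation. The sentence about Day 1 events without an onset time would then do nothing, since every Day 1 event would already be a TEAE. The SAP does use time elsewhere: SAP 5.5 defines post-baseline values by the date and time of first dose.

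A reader might infer more than the documents support:

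- *That pre-dose events will enter the tables.* They do so only if programming follows Appendix 1 literally.
- *That a co-primary comparison is compromised.* The documents do not use that term for safety. Adverse events are summarised as counts and percentages, and the hierarchical testing in SAP 4.3 covers only the primary efficacy endpoint.
- *That one SAE could dominate a table.* The patient would need an SAE from a pre-dose procedure and would still have to be dosed the same day, an unlikely sequence.
- *That Day 1 is full of pre-dose blood draws.* Only the PK sample is explicitly predose.

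**Conclusion.** The concern holds as an unresolved contradiction inside the current SAP (version 1.2). For a Day 1 event with a recorded pre-dose onset time, the known-start row of Appendix 1 gives a class that contradicts SAP 9.1 and protocol 9.4.2.1, and the SAP does not say which prevails.

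The severity is minor. On the assumed rates, the any-TEAE count rises by less than two patients per cohort. Pre-dose events arise before any treatment and under blinding, so they should be similar across arms. The result would be slightly inflated counts and a slightly diluted difference, with no reason to expect a bias towards either side. If few onset times are recorded the effect shrinks further, because both rules then default to TEAE. The case report form is not among the documents, so the share of Day 1 events with a usable time is unknown.

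**What to change.** In the known-start row of the treatment-emergence table in SAP Appendix 1, add a condition for events dated on the study drug start date:

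- onset time recorded and earlier than the first dose: not TEAE, and flagged as NTEAE if it is an SAE from a protocol-specified procedure;
- onset time recorded and the same as or later than the first dose: TEAE;
- onset time missing: TEAE.

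Leave the other rows unchanged. This carries out what SAP 9.1 and protocol 9.4.2.1 already say. The cost is one line in the SAP and one programming condition. Protocol 8.7 already requires the actual time of dosing to be recorded for the PK samples, and SAP 9.1 presupposes that some onset times are collected. Where they are not, the default remains TEAE and the change has no effect.
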